9.1.1.7 Visit 7 (Day 57)

This visit will occur 56 days after Visit 3 (randomization). A visit window of ± 3 days from the scheduled visit date is permitted, but it is preferred that the visit is performed on the scheduled visit day where possible.

The following observations will be made at Visit 7: concomitant medications (including AEDs), physical examination (including height and body weight), ECG, vital signs, epilepsy-related hospitalizations and AEs.

Study Code: GWEP1521
EudraCT Number: 2015-002154-12
Protocol V8 23Apr19

Clinical laboratory samples (blood and urine [where possible]), including pregnancy tests if appropriate (using both a serum sample and a urine dipstick), will be taken for hematology, biochemistry and urinalysis. Provided that the risk/benefit outcome is favorable in the investigator's opinion, prior to the first daily dose of IMP, a blood sample will be taken for analysis of plasma concentrations of concomitant AEDs.

Suicidality will be assessed in accordance with [Section 9.2.12.8](#).

The investigator must assess adherence to the dosing regimen by reviewing the patient's diary and IVRS data and record the patient's attendance at the visit.

All IMP (used and unused) will be collected and a check of the returned IMP against usage should be made. Patients will then receive new IMP.

9.1.1.8 Visit 8 (Day 71)

This visit will occur 70 days after Visit 3 (randomization). A visit window of ± 3 days from the scheduled visit date is permitted, but it is preferred that the visit is performed on the scheduled visit day where possible.

Visit 8 will be completed by telephone and will comprise a review of concomitant medications (including AEDs), epilepsy-related hospitalizations and AEs.

9.1.1.9 Visit 9 (Day 85)

This visit will occur 84 days after Visit 3 (randomization). A visit window of ± 3 days from the scheduled visit date is permitted, but it is preferred that the visit is performed on the scheduled visit day where possible.

The following observations will be made at Visit 9: concomitant medications (including AEDs), physical examination (including height and body weight), ECG, vital signs, epilepsy-related hospitalizations and AEs.

Clinical laboratory samples (blood and urine [where possible]), including pregnancy tests if appropriate (using both a serum sample and a urine dipstick), will be taken for hematology, biochemistry and urinalysis. Provided that the risk/benefit outcome is favorable in the investigator's opinion, prior to the first daily dose of IMP, a blood sample will be taken for analysis of plasma concentrations of concomitant AEDs.

Suicidality will be assessed in accordance with [Section 9.2.12.8](#).

The investigator must assess adherence to the dosing regimen by reviewing the patient's diary and IVRS data and record the patient's attendance at the visit.

Study Code: GWEP1521
EudraCT Number: 2015-002154-12
Protocol V8 23Apr19

All IMP (used and unused) will be collected and a check of the returned IMP against usage should be made. Patients will then receive new IMP.

9.1.1.10 Visit 10 (Day 113, End of Treatment/Withdrawal Visit)

This visit will occur 112 days after Visit 3 (randomization) or earlier if the subject withdraws from the study. A visit window of ± 3 days from the scheduled visit date is permitted, but it is preferred that the visit is performed on the scheduled visit day where possible. Patients will be instructed to record the dosing time of their concomitant AEDs in the diary.

The following observations will be made at Visit 10/the Withdrawal visit: concomitant medications (including AEDs), physical examination (including height and body weight), Tanner Staging (for patients aged 10–17 years [inclusive], or earlier if clinically indicated by onset of menarche or other signs of precocious puberty), details of menstruation (for females), ECG, vital signs, epilepsy-related hospitalizations and AEs.

Clinical laboratory samples (blood and urine [where possible]), including pregnancy tests if appropriate (using both a serum sample and a urine dipstick), will be taken for hematology, biochemistry, urinalysis, and determination of serum IGF-1 levels (for patients less than 18 years of age) to be performed by the central laboratory. Provided that the risk/benefit outcome is favorable in the investigator's opinion, prior to the first daily dose of IMP, a blood sample will be taken for analysis of plasma concentrations of concomitant AEDs. PK samples (patients > 20 kg in weight only) will be taken in accordance with [Section 9.2.9.1](#).

The following assessments will also be performed: QOLCE/QOLIE-31-P, PGIC, SGIC/CGIC, SGIC-SD/CGIC-SD, Wechsler Tests, CBCL/ABCL, SCQ and the Vineland-II. Suicidality will be assessed in accordance with [Section 9.2.12.8](#).

The investigator must assess adherence to the dosing regimen by reviewing the patient's diary and IVRS data, record the patient's attendance at the visit and confirm the outcome of the visit.

All IMP (used and unused) will be collected and a check of the returned IMP against usage should be made.

For patients 12 years of age and older who do not enter the taper period, the trained investigator or study coordinator will complete the Study Medication Use and Behavior Survey as an interview with the patient/caregiver.

Study Code: GWEP1521
EudraCT Number: 2015-002154-12
Protocol V8 23Apr19

For patients who withdraw early, the IVRS will be contacted to confirm withdrawal from the study. Patients who withdraw should have their dose of IMP tapered gradually (10% each day) over a period of 10 days, beginning at the time the decision is made to discontinue. In some cases, tapering the dose of IMP may be inadvisable (e.g., continued dosing is not possible due to an AE). The decision on whether or not to taper IMP will be left to the investigator's clinical judgment. If tapering is undertaken, a 10-day supply of IMP (if required) and instructions for tapering the dose will be provided. Patients/caregivers should continue to complete the IVRS (see APPENDIX 4) and paper diary and should return for Visit 11 (the 'End of Taper Period' visit), if possible.

Patients who have completed all of the scheduled study visits will be offered the option of entering an OLE. Entry is to be on the same day as Visit 10 (Day 113).

Patients not entering the OLE at this visit will be given a 10-day supply of IMP (if required) and instructions for tapering the dose, during which time IVRS (see APPENDIX 4) and paper diary information will continue to be recorded.

9.1.1.11 Visit 11 (Day 123, End of Taper)

This visit is required only for those patients who do not enter the OLE on the day of Visit 10 or for those who withdraw early and taper IMP. For patients who complete the study but opt not to enter the OLE, Visit 11 should occur 10 (+3) days after Visit 10 (i.e., on Day 123 [+3]). For patients who withdraw early and taper IMP, this visit should occur 10 (+3) days after the Withdrawal visit. For patients who begin to taper IMP but subsequently withdraw/do not complete the full taper period, this visit should occur on the final day of dosing or as soon as possible after this date.

The following observations will be made at Visit 11: concomitant medications (including AEDs), epilepsy-related hospitalizations and AEs, physical examination (including height and body weight), vital signs, ECG and clinical laboratory samples (blood and urine for hematology, biochemistry and urinalysis). Suicidality will be assessed in accordance with [Section 9.2.12.8](#).

For patients 12 years of age and older, the trained investigator or study coordinator will complete the Study Medication Use and Behavior Survey as an interview with the patient/caregiver.

The investigator must assess adherence to the dosing regimen by reviewing the patient's diary and IVRS data and record the patient's attendance at the visit.

Study Code: GWEP1521
EudraCT Number: 2015-002154-12
Protocol V8 23Apr19

All IMP (used and unused) will be collected and a check of the returned IMP against usage should be made. The patient diaries will be collected.

Following Visit 11 (or date of final dosing) the IVRS seizure reporting diary should only be completed once more (see APPENDIX 4).

9.1.1.12 Visit 12 (Day 151, Safety Follow-up)

This visit is required for patients who do not enter the OLE or who withdraw from the study early. This visit should occur four weeks after Visit 11 (+3 days), or date of final dosing, and can be conducted over the telephone. The following observations will be made at Visit 12: concomitant medications (including AEDs), epilepsy-related hospitalizations and AEs.

9.1.2 Open-label Extension

Patients who successfully complete the blinded phase will be invited to participate in the OLE when they reach the End of Treatment visit (Visit 10) of the blinded phase. They will be issued with the OLE patient information and informed assent or the patient/parent(s)/legal representative information and informed consent (as applicable). Following adequate time to discuss the study with the investigator, nurse, relatives or caregiver, patients/parent(s)/legal representatives who provide written informed consent/assent at Visit B1 will be enrolled into the OLE. The OLE period will last for a maximum of 1 year; however, patients in the US and Poland may have the opportunity to continue in the OLE beyond this.

On-label use of mTOR inhibitors (for the treatment of seizures or tumors) and general anesthesia are permitted in the OLE phase of the trial.

9.1.2.1 Visit B1 (Day 1)

Day 1 is regarded as the first day of IMP dosing. The following data collected at the 'End of Treatment' visit of the blinded phase will also be considered as Visit B1 data: vital signs, physical examination (including height and body weight), details of menstruation (for females), Tanner Staging (patients aged 10–17 [inclusive]), ECG, clinical laboratory samples (blood and urine for hematology, biochemistry, urinalysis, determination of serum IGF-1 levels [patients less than 18 years of age], and pregnancy tests [if appropriate]), IVRS and paper diary information from the blinded phase (including information regarding seizures, AEs, usage of rescue medication, concomitant AEDs, IMP dosing), epilepsy-related hospitalizations, AEs, concomitant medications and/or changes to medication, QOLCE/QOLIE-31-P, PGIC,

Study Code: GWEP1521
EudraCT Number: 2015-002154-12
Protocol V8 23Apr19

SGIC/CGIC, SGIC-SD/CGIC-SD, Wechsler Tests, CBCL/ABCL, SCQ and the Vineland-II. Suicidality will be assessed in accordance with [Section 9.2.12.8](#).

Patients will take their final dose of the blinded phase IMP in the morning of Visit B1, followed by collection of the blinded phase 'End of Treatment' assessments. Patients will be instructed to begin the Blinded Open-label transition, taking their first dose of Blinded Transition OLE IMP in the evening of Visit B1 (Day 1).

Patients or their caregivers will receive sufficient IMP for two weeks' home dosing together with a blinded transition phase. If an unacceptable AE develops at any time during transition, dosing should initially be suspended or amended, at the investigator's discretion, until the event has resolved or is well tolerated.

Patients or their caregivers will be given a paper diary to record information regarding AEs, IMP, usage of rescue medication, concomitant AEDs and IMP dosing. In addition, patients/caregivers will be instructed to complete a weekly seizure reporting diary until the Follow-up visit using the IVRS.

The investigator should review the laboratory results as soon as these become available. If the results raise any safety concerns, the investigator should consider whether it will be appropriate for the patient to continue to participate in the extension study, or if the patient should be withdrawn.

In order to complete the SGIC/CGIC, the patient/caregiver is to compare to the memory aid from the Baseline of the blinded phase. If the memory aid is not available from the Baseline of the blinded phase then the patient/caregiver should do this from memory, if possible, and complete a memory aid at Visit B1.

In order to complete the SGIC-SD/CGIC-SD, the patient/caregiver would have been asked to assess and note the average duration of the patient's seizures at the Baseline of the blinded phase as a memory aid for subsequent visits. If the memory aid is not available from the Baseline of the blinded phase then the patient/caregiver should do this from memory, if possible, and complete a memory aid at Visit B1.

Following Visit B1, during the blinded transition, safety telephone calls must be made every two days. If the call falls on a weekend, it is permitted to schedule the call for the Friday before or Monday after the weekend instead. During these calls, caregivers will be asked for information on AEs, epilepsy-related hospitalizations, concomitant medications and/or changes to medication. The investigator must retain oversight of safety telephone calls.

Study Code: GWEP1521
EudraCT Number: 2015-002154-12
Protocol V8 23Apr19

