	
for:
 
 - Hematology - Biochemistry - Urinalysis - Urine/serum pregnancy tests (Visits 5, 7, 9 and 10, if appropriate) - Serum IGF-1 (Visit 10) - PK (Visit 10; patients > 20 kg only) - AED concentrations (Visits 5, 7, 9 and 10) 
 • Review of patient diary • IMP dispensing, collection and compliance review 
PK:
 
Blood sample collection for PK analysis of CBD and its major metabolites will be taken at Visits 3 and 10 for patients weighing more than 20 kg. Where appropriate, blood samples will be taken as follows:
 
 • One sample pre-dose (i.e., prior to administration of IMP). • One sample between 2 and 3 hours post-dose. • One sample between 4 and 6 hours post-dose. • One sample between 8 and 10 hours post-dose (patients 18 years and above only). 
Blood samples will be collected for analysis of plasma concentrations of concomitant AEDs (if possible) ideally at the following time points:
 
 • Visit 3 - Pre-IMP-dose. • Visit 5 - Pre-IMP-dose. • Visit 7 - Pre-IMP-dose. • Visit 9 - Pre-IMP-dose. • Visit 10 - Pre-IMP-dose. 
Additional blood samples may be taken for AED monitoring if there is a suspicion of changes in AED levels, with the aim to keep the AED plasma levels within the patient's therapeutic level.
 
Open-label Extension Transition and Open-label Extension:
 
Following completion of the blinded phase of the study, patients will enter a 2-week blinded transition followed by a 3-week titration. Safety telephone calls will be conducted every two days during this 5-week period and one week after the end of titration. If the call falls on a weekend, it is permitted to schedule the call for the Friday before or Monday after the weekend instead. OLE visits will occur on Day 15, Day 36, Day 92 and then every 13 weeks up to 1 year. Additional IMP Re-supply Visits will be

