9.2.9.1 Pharmacokinetic Blood Sampling

The plasma concentration/time curves of CBD and its major metabolites will be assessed at Visits 3 and 10 for patients weighing more than 20 kg. Where appropriate, blood samples will be taken as follows:

- One sample pre-dose (i.e., prior to administration of IMP).
- One sample between 2 and 3 hours post-dose.
- One sample between 4 and 6 hours post-dose.
- One sample between 8 and 10 hours post-dose (patients 18 years and above only).

There must be a minimum period of at least two hours between each of the blood sampling time points. In the event of an AE that, in the opinion of the investigator, is related to a concomitant AED, additional blood samples may be collected.

For patients who undergo PK blood sampling, the patient/caregiver will record all meal times and the types of meals consumed by the patient during all PK testing days (Visits 3 and 10).

Analysis of all pharmacokinetic samples will be conducted at a central clinical laboratory. Sample volume requirements and processing procedures will also be detailed in a separate laboratory manual.

Study Code: GWEP1521
EudraCT Number: 2015-002154-12
Protocol V8 23Apr19

The patient/caregiver must be advised that it may not be safe for them to undertake further blood tests within one month of any study-related blood draws and to inform the investigator if they suffered any blood loss during the one-month period leading up to a planned blood draw.

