9.2.9.2 Determination of Plasma Concentrations of Concomitant Antiepileptic Drugs

Plasma concentrations of concomitant AEDs will be assessed at Visits 3, 5, 7, 9 and 10/ the Withdrawal visit (if possible) during the blinded phase and at Visits B2, B3, B4 and all subsequent Assessment Visits during the OLE. Samples will be collected for all patients provided that the risk/benefit outcome is favorable in the investigator's opinion. At each visit, blood samples will be taken prior to administration of IMP. Patients will be instructed to record the dosing time of their concomitant AEDs in the diary.

Additional blood samples may be taken for AED monitoring if there is a suspicion of changes in AED levels, with the aim to keep the AED plasma levels within the patient's therapeutic level. AED doses should be adjusted, as appropriate, following discussion with the GW medical monitor in order to maintain stable AED plasma concentrations.

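### For patients entering the OLE, the protocol gives two incompatible orders of IMP dose and blood sampling on the Visit 10/Visit B1 day

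*Protocol*

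**What the plan says.** Section 9.1.1.10 offers the extension to patients who have completed all scheduled visits and fixes when they start it: "Entry is to be on the same day as Visit 10 (Day 113"). For these patients Visit 10 and Visit B1 are therefore one attendance.

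The protocol then describes that day in two ways.

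- **Dose first.** Section 9.1.2.1: "Patients will take their final dose of the blinded phase IMP in the morning of Visit B1, followed by collection of the blinded phase". What is collected after the dose is the set of End of Treatment assessments. The next dose, the first of the blinded transition, is taken that evening.
- **Blood first.** For AED levels at Visit 10, Section 9.1.1.10 says that "prior to the first daily dose of IMP, a blood sample will be taken for analysis of plasma concentrations of concomitant AEDs". Section 9.2.9.2 makes this general: "At each visit, blood samples will be taken prior to administration of IMP". The synopsis lists "Visit 10 - Pre-IMP-dose". For PK, Section 9.1.1.10 says "PK samples (patients > 20 kg in weight only) will be taken in accordance with" Section 9.2.9.1, and the sampling list in that section opens with "One sample pre-dose (i.e., prior to administration of IMP").

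The blinded-phase schedule in Appendix 1 puts both PK sampling and AED concentration at Visit 10.

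**The concern.** The same morning dose cannot come both before and after the same blood sample. Staff handling a patient who rolls over would reasonably turn to Section 9.1.2.1, which covers that attendance, and its order leaves no room for a pre-dose draw.

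The PK loss matters because nothing else replaces it. Plasma CBD and its metabolites "will be assessed at Visits 3 and 10 for patients weighing more than 20 kg". Visit 3 is the first-dose visit, and the PK endpoint is confined to the blinded phase. Visit 10 is thus the only multiple-dose PK visit. Its pre-dose sample is the only CBD measurement taken just before a dose while the patient is on treatment, and it supplies the time-zero value for AUC0-t.

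For AEDs the loss is one of comparability. The exploratory objective is the effect of GWP42003-P on concomitant AED concentrations. A last time point drawn after IMP would be set against earlier ones drawn before it. If some sites follow one section and some the other, the Visit 10 data are a mixture. An analysis plan cannot recover a sample that was never drawn.

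**Working it through.** The plan states no figure on this point. The check compares the texts and counts the samples.

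**Do the two orders meet in the same patient?** Yes. Extension entry is on the Visit 10 day (Section 9.1.1.10), so an entrant has one morning IMP dose to which both rules apply.

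**Are the PK and AED samples among the assessments that Section 9.1.2.1 places after the dose?** Its ordering sentence refers to the blinded-phase End of Treatment assessments as a whole. Section 9.1.1.10 and the Appendix 1 schedule include AED concentration and PK at that visit. The separate list in Section 9.1.2.1 of data shared with Visit B1 names neither, but that list does not limit the ordering sentence.

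**Does any current text reconcile the two?** None was found. Section 9.1.2.1 makes no exception, and the sampling sections make none for extension entrants.

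**What is lost where Section 9.1.2.1 is followed to the letter?**

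- *PK samples at Visit 10, patients 18 and over and above 20 kg.* Planned: pre-dose, 2–3 h, 4–6 h and 8–10 h, so 4. Without the pre-dose sample: 4 − 1 = 3.
- *PK samples at Visit 10, patients under 18 and above 20 kg.* Planned: pre-dose, 2–3 h and 4–6 h, so 3. Without the pre-dose sample: 3 − 1 = 2.
- *On-treatment pre-dose CBD samples in the whole trial, per patient.* The PK visits are 3 and 10. The Visit 3 pre-dose sample precedes any IMP, because the first dose is taken at Visit 3 (Section 8.1.2). Planned: 1. Left: 1 − 1 = 0.
- *Blinded-phase AED samples drawn before IMP.* Planned at Visits 3, 5, 7, 9 and 10, so 5. Left: 5 − 1 = 4. The Visit 10 sample would still exist, but it would be drawn after IMP.

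**What follows for the endpoints?** The AUC0-t endpoint runs from time zero to the last measurable time point. At Visit 10 its first value would be missing, so the area would have to be left out or rest on an imputed value. The AED series would keep four draws taken under one condition and a fifth taken under another.

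**How many patients?** The PK loss is confined to extension entrants above 20 kg; the AED point reaches extension entrants of any weight. The protocol does not forecast how many will enter the extension, how many exceed 20 kg, or which section sites will follow, so no patient count can be given.

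**The case against.** The best reply is that specific rules prevail over a general sentence. Four places say that the Visit 10 AED or first PK sample comes before IMP. The one sentence that points the other way does not mention PK or AED levels, and the extension schedule shows no AED concentration at Visit B1. The rationale to Amendment 5 also lists a pre-dose sample among the required Visit 10 PK draws, so the intent is plain. A site that follows Sections 9.1.1.10 and 9.2.9.1 samples as intended. This stands as far as it goes: the protocol does not fix a wrong order, it gives two. It does not remove the conflict, because Section 9.1.2.1 addresses the very attendance at issue.

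The sampling is also qualified. PK draws are to be made where appropriate. AED draws depend on feasibility and on the investigator's view of risk and benefit, and the synopsis timings are described as ideal. AUC0-t is calculated only where the data allow. These qualifiers lower the stakes. They allow for an occasional missing sample, but they do not settle which order applies.

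A reader might infer more than the documents support:

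- *That the Visit 10 samples will be post-dose in all extension entrants.* This follows only where a site lets Section 9.1.2.1 override the sampling sections, and for PK only above 20 kg.
- *That the dose is taken at home and its time is merely recalled.* Section 9.1.2.1 does not say where the dose is taken. CRF and laboratory-manual content is not shown, so a missing dose time cannot be inferred.
- *That the trough would be overstated, or AUC lost, by a definite amount.* The protocol gives no PK parameters, so any such figure would rest wholly on assumptions. Concentrations are summarised by time window, so the likelier result is a missing pre-dose value than a mislabelled one.

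**Conclusion.** The inconsistency is real in the current text and worth correcting, but it is narrow. For extension entrants the protocol gives two incompatible orders of dose and sampling on one day, and those passages must be reconciled.

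Where Section 9.1.2.1 is followed, the loss of the multiple-dose pre-dose CBD sample is complete for entrants above 20 kg. The AED loss is partial, since Visits 3, 5, 7 and 9 are untouched. Whether a post-IMP draw would shift the AED results is not shown. The rules fix sampling relative to IMP, while AED dosing times are recorded separately.

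Only the exploratory PK and AED-concentration endpoints are touched. The primary and key secondary analyses, the Type I error control and the sample size are not affected. The conclusion rests on one assumption: that at least some sites would work from Section 9.1.2.1 on the roll-over day.

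**What to change.** Add one sentence to Section 9.1.2.1 stating that the blood samples defined as pre-dose in Sections 9.1.1.10, 9.2.9.1 and 9.2.9.2 are exempt from its dose-then-assessments order, so that a single sampling order applies on the Visit 10/Visit B1 day whether or not the patient enters the extension. Send sites a short reminder.

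The change alters no dose, dosing schedule or visit and adds no sample. It settles only when blood already planned is drawn relative to a dose already planned. The cost is one sentence in the next amendment and the reminder.
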